Appendix 5. Part B/C Pharmacokinetic Assessment Timepoints

Study Day/Week	Protocol Time	PK Blood	Safety ECGs
Screening			X
Day 1	Predose	X ^a	X
	Dose		
	1 hour	X	
	2 hours	X	
	4 hours	X	X
	8 hours	X	X
Day 2	24 hours	X	X
Week 1		X	
Week 4	Predose	X ^a	X
	Dose		
	1 hour	X	
	2 hours	X	
	4 hours	X	X
	8 hours	X	
	24 hours	X	
Week 5		X	

^a At ≤ 15 minutes prior to dosing

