9.2 Plasma PK Parameters

Pharmacokinetic analysis will be performed on the plasma PK concentration data to determine PK parameters by non-compartmental analysis using Phoenix WinNonlin® software (version 8.1 or higher).

Actual sampling times will be used for the PK analysis and if the actual sampling time is not recorded, the nominal sampling time will be used.

PK parameters (applicable for single dose cohorts in part A, day 1-dose and day-29 dose of multiple dose cohorts in part B and C):

Due to the short plasma half-life of VIR-2218 and metabolite, pharmacokinetic analysis will be performed separately for day-1 dose and day-29 dose in patients in parts B/C.

The following PK parameters of VIR-2218 and its metabolites to be determined at defined timepoints include:

- **C_{max}** : Individual maximum concentration (C_{max}) values are directly determined from the plasma concentration time profiles for each subject.
- **t_{max}** : The time to attain C_{max} . If the same C_{max} concentration occurs at different time points, t_{max} is assigned to the first occurrence of C_{max} .
- **t_{last}** : Time of last measurable (positive) observed concentration

- **C_{last}**: Observed concentration corresponding to t_{last}.
- **AUC_{0-t}**: The areas under the curve spanning time interval from 0 to t (up to the last time point with measurable concentration). AUC_{0-t} will be calculated using the linear-up /logarithmic-down trapezoidal rule.

Linear trapezoidal rule:

The area of the trapezoid between the two data points (t₁, C₁) and (t₂, C₂) where C₂ ≥ C₁ will be computed by:

$$AUC_{t_1-t_2} = 0.5(t_2 - t_1)(C_1 + C_2)$$

Logarithmic trapezoidal rule:

The area of the trapezoid between the two data points (t₁, C₁) and (t₂, C₂) where C₂ < C₁ will be computed by:

$$AUC_{t_1-t_2} = \frac{((t_2 - t_1)(C_1 - C_2))}{\ln C_1 - \ln C_2}$$

- **AUC_{0-12hr}**: The area under the plasma concentration-time curve over the time interval from 0 to 12 hr using the linear-up /logarithmic-down trapezoidal rule.
- **AUC_{0-24hr}**: The area under the plasma concentration-time curve over the time interval from 0 to 24 hr using the linear-up /logarithmic-down trapezoidal rule.
- **AUC_{0-∞}**: The area under the plasma concentration-time curve over the time interval from 0 extrapolated to infinity will be calculated according to the following equation:

$$AUC_{0-\infty} = AUC_{0-t} + \frac{C'_t}{\lambda_z}$$

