where C'_t is the predicted concentration at the time t (last time point with a measurable plasma concentration above the quantification limit) at which quantification was still possible, the calculation of λ_z is given below.

- **AUC_{%extrap}**: The percentage of the AUC that has been extrapolated beyond the last observed data point, calculated as:

$$AUC_{\%extrap} = \left(\frac{AUC_{0-\infty} - AUC_{0-t}}{AUC_{0-\infty}} \right) * 100$$

- **λ_z**: The apparent terminal rate constant λ_z will be estimated from a regression of ln(C) versus time over the terminal log-linear drug disposition portion of the concentration-time profiles. To calculate the elimination rate constant, the terminal data from a concentration-time curve will be used. Starting with the final non-BLQ data point and moving backwards, toward time zero, at least 3 data points not included C_{max} are fit to a linear regression. The number of data points used can be determined by maximizing the value adjusted-r² which defines the “best-fit” of the data.

The first order rate constant associated with the terminal (log-linear) portion of the curve will be estimated via linear regression of time vs. log concentration. The rules are that a minimum of three points is needed to define the terminal (log-linear) portion of the

curve, λ_z must be positive, and the selection is based on the best adjusted

square coefficient of regression (r^2). Additionally, if the adjusted r^2 does not improve, but is within 0.0001 of the largest adjusted R^2 value, the regression with the larger number of points is used.

The “adjusted” r^2 is calculated using the following equation:

$$\bullet \quad Adjusted\ r^2 = 1 - (1 - r^2) * \frac{(n-1)}{(n-2)},$$

where n = the number of data points used in the regression.

The slope of the line is equal to $-\lambda_z$ (i.e., the slope will be negative, but λ_z is a positive value).

If terminal concentration-time point(s) increases, this time point may be included if the $t_{1/2}$ estimate is reasonable. If λ_z is not determinable (for example, adjusted- r^2 value <0.8) then consequently only parameters not requiring λ_z will be reported. In addition, the lower (R_{start}) and upper (R_{end}) limit on time (h) for values to be included in the calculation of λ_z will be listed.

- **$t_{1/2}$:** The terminal half-life will be calculated from the terminal rate constant using the equation:

$$T_{1/2} = \frac{Ln(2)}{\lambda}$$

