- **CL/F:** The total clearance will be calculated as following:

$$CL/F = \frac{D}{AUC_{0-\infty}}$$

where D is dose.

- **V_z/F:** The apparent volume of distribution based on terminal phase will be calculated according to the following equation:

$$V_z/F = \frac{CL/F}{\lambda_z}$$

Other important PK considerations

- The value of $AUC\%_{extrap}$ will be less than or equal to 20% for the $AUC_{0-\infty}$ to be considered well estimated. If this proportion is > 20%, then the values of $AUC_{0-\infty}$ will be treated with caution, and emphasis will be placed on AUC_{0-t} values (i.e. in subsequent statistical analyses).
- If $AUC\%_{extrap} > 20\%$, all elimination related parameters (λ_z , $AUC_{0-\infty}$, $t_{1/2}$, CL/F or CL/F_{ss} , and V_z/F or V_z/F_{ss}) will be presented in the listings but excluded from the calculation of summary statistics. All values excluded from the summaries should be flagged in the individual listings with an explanation for the exclusion.
- If data permits, the other PK parameters may be reported.
- If $t_{last} = t_{max}$, C_{max} will not be reported for that subject in the listings. It will be footnoted to indicate that sampling timepoints were not appropriate for that subject.
- If $t_{last} < 24hr$, AUC_{0-24hr} will only be reported when $AUC\%_{extrap} < 20\%$; It will be presented in the listing with footnote to indicate that AUC_{0-24hr} was extrapolated. In the summary

tables, the cohort will be footnoted to indicate that subjects with extrapolated AUC_{0-24hr} were included in the calculation of summary statistics.

- If $t_{last} < 12hr$, AUC_{0-12hr} will only be reported when $AUC\%_{extrap} < 20\%$; It will be presented in the listing with footnote to indicate that AUC_{0-12hr} was extrapolated. In the summary tables, the cohort will be footnoted to indicate that subjects with extrapolated AUC_{0-12hr} were included in the calculation of summary statistics.

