9.6 DOSE PROPORTIONALITY FOR PK PARAMETERS

Dose proportionality will be evaluated separately for healthy subjects (part A) and day-1 dose of CHB subjects (part B and C) based on subjects without dosing deviations.

To assess dose proportionality, the natural log transformed, dose normalized $AUC_{0-\infty}$, AUC_{0-t} , AUC_{0-12} , AUC_{0-24} and C_{max} parameters will be evaluated using power model [2], with VIR-2218 dose level as the independent variable.

The power model for assessment of dose proportionality has the form of $\log(y) = \log(\beta_0) + \beta_1 \log(Dose)$ where y represents the PK parameter of interest. Dose proportionality is concluded if 90% CI for the β_1 falls within 0.7 to 1.43, which is less than 30% difference between doses for a given PK parameter.

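### The AUC0-24 reporting rule compares the actual time of the last quantifiable sample with exactly 24 h, so a 24 h sample drawn minutes early can cause AUC0-24 to be withheld although almost none of the area is missing

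*SAP*

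**What the plan says.** The elements are spread over several places.

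- **Reporting rule** (SAP 9.2 Plasma PK Parameters, other considerations): "If $t_{last} < 24hr$, AUC_{0-24hr} will only be reported when $AUC\%_{extrap} < 20" per cent. The parallel rule is "If $t_{last} < 12hr$, AUC_{0-12hr} will only be reported when $AUC\%_{extrap} < 20" per cent. Values reported under either rule are footnoted as extrapolated.
- **Time basis** (same section): "Actual sampling times will be used for the PK analysis". Nominal time is the fallback only when the actual time was not recorded. t_last is defined as "Time of last measurable (positive) observed concentration", so it is an actual time.
- **Lambda-z** (same section): "at least 3 data points not included C_{max} are fit to a linear regression", and "a minimum of three points is needed to define the terminal (log-linear) portion". If lambda-z is not determinable, for example with adjusted r2 below 0.8, parameters that need it are not reported. AUC%extrap is one of these, because it is computed from AUC0-inf.
- **BLQ values** (SAP 9.1): after the first quantifiable concentration they are set to missing.
- **Sampling** (Protocol Appendix 5, "Part B/C Pharmacokinetic Assessment Timepoints"): after the Day 1 dose, plasma is drawn at 1, 2, 4, 8 and 24 h and at Week 1. The only tolerance stated is for the predose sample.
- **Use** (SAP 9.6): "Dose proportionality will be evaluated separately for healthy subjects (part A) and day-1 dose of CHB subjects (part B and C"), with AUC0-24 among the five parameters modelled.

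SAP 9.2.1 calculates and lists deviations between nominal and actual sampling times, but does not use them as a tolerance.

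**The concern.** The rule makes sense for a profile that ends well before 24 h and needs real extrapolation. Taken literally, it also catches a profile that was sampled at the nominal 24 h point with a quantifiable result, when the tube was filled at, say, 23.9 h. Two subjects with the same concentrations are then treated differently: one drawn at 24.0 h has AUC0-24 reported unconditionally, and one drawn at 23.9 h must pass a test on AUC%extrap.

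That test asks the wrong question in this case. AUC%extrap is the share extrapolated to infinity, not the share missing before 24 h, and it does not exist without lambda-z. Part B/C cohorts have 3 active subjects before any expansion (4 randomized 3:1), so each withheld value removes a third of that cohort's AUC0-24 data. The loss is also not random. It falls on profiles with a later tmax, so the AUC0-24 summary would rest on the earlier-peaking subjects.

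**Working it through.** The plan states no frequency for this rule, so there is no figure of its own to reproduce.

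**1. Can lambda-z be estimated?** Count the samples after Cmax when the 24 h sample is the last quantifiable one. Three are needed.

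| Sampled tmax | Points left, Part B/C | Points left, Part A |
|---|---|---|
| 1 h | 4 | 7 |
| 2 h | 3 | 6 |
| 4 h | 2 | 5 |
| 8 h | 1 | 3 |

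In Part B/C lambda-z is impossible by count from a sampled tmax of 4 h, and rests on the bare minimum at 2 h. In Part A the count is adequate up to 8 h. If the Week 1 sample is quantifiable, t_last is about 168 h and the rule is not triggered.

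**2. Worked record (illustrative values).** Concentrations 0, 100, 180, 250, 160 and 10 at 0, 1, 2, 4, 8 and 23.9 h, with the SAP's linear-up/log-down rule:

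- 0-1 h: 0.5 × 1 × (0 + 100) = 50
- 1-2 h: 0.5 × 1 × (100 + 180) = 140
- 2-4 h: 0.5 × 2 × (180 + 250) = 430
- 4-8 h: 4 × (250 − 160) / ln(250/160) = 806.7
- 8-23.9 h: 15.9 × (160 − 10) / ln(160/10) = 860.2

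The sum is 2287. The missing 0.1 h adds at most 0.1 × 10 = 1.0, or 1.0/2287 = 0.04%. Only two points follow Cmax, so AUC%extrap is undefined and AUC0-24 is not reported.

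**3. Unobserved area in general.** One-compartment absorption model; assumed half-life 3-16 h and absorption half-life 1 or 3 h:

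| 24 h sample early by | Share of AUC0-24 unobserved |
|---|---|
| 5 min | 0.01-0.28% |
| 15 min | 0.04-0.83% |
| 30 min | 0.07-1.7% |

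**4. Second route to withholding.** In the same model, with the sample 5 min early, AUC%extrap is 0.6-20% for half-lives of 3-8 h but 27-44% for 12-16 h. In the latter range AUC0-24 is withheld even though lambda-z exists.

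**5. Frequency, Part B/C.** Simulation with the 24 h sample 5 min early, 25% log-normal error, LLOQ 1% of Cmax, half-life 3, 5 or 8 h and the SAP lambda-z rule. All of these inputs are assumptions. Rates are among profiles whose last quantifiable sample is the 24 h one. The last column halves the sum of the two routes, assuming that half of draws are early.

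| True tmax | Lambda-z not estimable | AUC%extrap ≥ 20% | Withheld if half are early |
|---|---|---|---|
| 1.5 h | 3-25% | 0-10% | 1.5-17.5% |
| 3 h | 52-58% | 0-10% | 26-34% |
| 4 h | 75-79% | 0-8% | 37.5-43.5% |
| 6 h | 95-96% | 2-4% | 49-49.5% |

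For example, at tmax 4 h and half-life 8 h: 0.5 × (0.79 + 0.08) = 43.5%. A separate simulation with variable draw times (SD 0.1-1 h, 15% error, LLOQ 0.5% of Cmax) gave 11-22%, 38-42% and 42-49% at typical tmax 2, 4 and 6 h. At typical tmax 1 h (SD 0.1 h) the rate was about 0-3% for half-lives of 3-5 h and 12% for 8 h.

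**6. Per cohort of 3 active subjects.** If a fraction w is withheld, the chance of losing at least one value is 1 − (1 − w)^3. At w = 1.5% this is 1 − 0.985^3 = 4.4%; at w = 49.5% it is 1 − 0.505^3 = 87.1%.

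**The case against.** The strongest reply is that the rule, though loosely worded, seldom matters and costs little when it does. Much of this stands.

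- **Frequency is unknown.** The documents give no tmax, no LLOQ and no half-life value; the SAP says only that the plasma half-life is short. A reader might infer from the sparse Part B/C schedule that withholding will be common. That does not follow: with an early tmax it is rare. It also requires the 24 h sample to be quantifiable. With half-life 3 h, typical tmax 2 h and an LLOQ of 2% or 5% of Cmax, only 20% or 2% of simulated profiles ended at that sample, and about 3% or 1% of all profiles lost AUC0-24. The one-half early figure is itself an assumption.
- **The exposure data are not lost.** In the worked record, 2287 is still reported as AUC0-t. Cmax remains, and so does AUC0-12, because 23.9 h is not below 12 h. SAP 9.6 models these as well. The protocol endpoints name AUC to the last measurable timepoint and to infinity, and the study is descriptive.
- **AUC0-12 is barely affected.** The wording is parallel, so a reader might infer the same fault throughout. Part B/C has no 12 h sample, so a 12 h draw taken minutes early cannot occur there. In Part A it matters only if the 24 h sample is BLQ, and three points then remain for a sampled tmax up to 6 h. Simulated withholding was 0-10% of profiles, below 4% in most settings.
- **The Week 4 dose may escape.** Footnote r of Protocol Appendix 3, read literally, times that sample 24 h after the first post-dose draw, which is nominally at 1 h, hence about 25 h after the dose. Appendix 5 lists 24 h.
- **The gate is conservative for early-ending profiles.** The share extrapolated to 24 h can never exceed AUC%extrap, so there is no need to replace the gate for those profiles.

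What remains is that the rule, followed as written, discards a value that is known almost exactly. The SAP also gives no way to close a gap of a few minutes without lambda-z.

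**Conclusion.** The fault is real and can be read from the text: an actual-time t_last is compared with exactly 24 h without tolerance, and the fallback condition may be unmeetable. The area at issue is about 0.01-0.3% of AUC0-24 at 5 minutes early and at most 1.7% at 30 minutes (assumed half-life 3-16 h). In Part B/C the count alone rules out lambda-z for any sampled tmax of 4 h or later when the 24 h sample is last.

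Among such profiles the share withheld runs from near 0% (early tmax) to about 50% (tmax 4-6 h), given the assumed half-lives, LLOQ and half of draws early. The consequence is limited to AUC0-24 summaries and the AUC0-24 input to the dose-proportionality model, which uses the Day 1 dose in Part B/C. The documents do not support reading this as a threat to a primary endpoint, or as a loss of a third of a cohort's exposure information; only the AUC0-24 value is lost. For AUC0-12 the point is confined to Part A profiles with a BLQ 24 h sample. For the Week 4 dose it cannot be settled until the two protocol passages agree.

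**What to change.** In SAP 9.2 (Plasma PK Parameters), amend the two t_last bullets:

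1. If the nominal 24 h (12 h) sample is quantifiable and was drawn within a pre-specified tolerance of nominal time, report AUC0-24 (AUC0-12) without the AUC%extrap condition. A tolerance of 5% would be one choice: 0.05 × 24 = 1.2 h, and 0.05 × 12 = 0.6 h.
2. Close any short remaining gap with lambda-z where available, otherwise with the log-linear slope of the last two points, and flag the value in the listing.
3. Keep the existing AUC%extrap < 20% rule for profiles that end at an earlier nominal time or outside the tolerance.

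Separately, reconcile footnote r of Protocol Appendix 3 with Appendix 5 on the timing of the 24 h sample after the Week 4 dose.

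The cost is SAP wording and a few lines of PK programming, with no new data. The downside is a small extrapolated piece in some values, about 1% or less in most cases. At the edge of a 1.2 h tolerance it would be larger. Scaling the 30-minute shares by 1.2/0.5 gives about 1.07% × 2.4 = 2.6% at half-life 8 h and 1.67% × 2.4 = 4.0% at 16 h (absorption half-life 3 h), so a tighter limit may be preferred if the half-life proves long.

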9.5 Urine PK Parameters

The following urine PK parameters of VIR-2218 and its metabolites will be determined for all single dose and multiple dose cohorts/parts:

- **Ae_{t1-t2}**: Total amount of drug excreted in urine from time t1 to t2 hours (cumulative and for each specific urine time intervals)
- **CLr**: Renal clearance of drug (cumulative) calculated as:

$$CLr = \frac{Ae_{t1-t2}}{Plasma\ AUC_{t1-t2}}$$

- **fe**- Fraction of the administered drug excreted into the urine (cumulative and for each specific urine time intervals)

$$fe = \left(\frac{Urinary\ excreted\ amount(mg)}{Dose(mg)} \right) * 100$$

9.6 DOSE PROPORTIONALITY FOR PK PARAMETERS

Dose proportionality will be evaluated separately for healthy subjects (part A) and day-1 dose of CHB subjects (part B and C) based on subjects without dosing deviations.

To assess dose proportionality, the natural log transformed, dose normalized $AUC_{0-\infty}$, AUC_{0-t} , AUC_{0-12} , AUC_{0-24} and C_{max} parameters will be evaluated using power model [2], with VIR-2218 dose level as the independent variable.

The power model for assessment of dose proportionality has the form of $\log(y) = \log(\beta_0) + \beta_1 \log(Dose)$ where y represents the PK parameter of interest. Dose proportionality is concluded if 90% CI for the β_1 falls within 0.7 to 1.43, which is less than 30% difference between doses for a given PK parameter.

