2.5 Randomization

An Interactive Web Response System (IWRS) will be employed to manage subject randomization and treatment assignments.

Four dose-level cohorts are planned for Part A: 50 mg, 100 mg, 200 mg, and 400 mg. Two sentinel subjects will be randomized 1:1 to VIR-2218 or placebo. These subjects will be dosed concurrently and monitored for 24 hours; if the investigator has no safety concerns, the remainder of the subjects in the same cohort will be dosed. The remaining subjects will be randomized 5:1 to VIR-2218 or placebo.

Two optional cohorts in Part A may be added following the same stratification, including sentinel dosing, up to a maximum dose of 900 mg. In addition to the optional cohorts, a total of 8 “floater” subjects may be added to expand any cohort in Part A. “Floater” subjects are to be added in increments of 4 and randomized 3:1 to VIR-2218 or placebo.

Three dose-level cohorts are planned for Part B: 50 mg, 100 mg, and 200 mg. One dose-level cohort is planned for Part C: 200 mg. Each cohort in Part B/C will be randomized 3:1 to VIR-2218 or placebo.

Two optional cohorts in Part B and 2 optional cohorts in Part C may be added following the same stratification, up to a maximum dose of 450 mg per dose (900 mg cumulative dose). In addition to the optional cohorts, a pool of 16 “floater” subjects may be added to expand any cohort in Part B and/or C if further data are needed. “Floater” subjects are to be added in increments of 4 (3:1) to maintain the randomization ratio.

In Parts A-C, blinding of study treatment will be managed by the clinical investigative site’s pharmacy in accordance with the Pharmacy Manual. In the event of a medical emergency where breaking the blind is required to provide medical care to the subject, the investigator may obtain treatment assignment for that subject. IWRS should be used as the primary method of breaking the blind. If IWRS cannot be accessed, the investigator should contact the Sponsor medical monitor to break the blind. Treatment assignment should remain blinded unless that knowledge is necessary to guide subject emergency medical care. The investigator is requested to contact the Sponsor medical monitor promptly in case of any treatment unblinding.

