3.6 Cohorts (Treatment Groups)

Part A (SAD):

- VIR-2218 50 mg
- VIR-2218 100 mg
- VIR-2218 200 mg
- VIR-2218 400 mg
- VIR-2218 600 mg
- VIR-2218 900 mg
- VIR-2218 Overall
- Placebo
- Overall

Part B (MAD – HBeAg-):

- VIR-2218 20 mg
- VIR-2218 50 mg
- VIR-2218 100 mg
- VIR-2218 200 mg
- VIR-2218 Overall
- Placebo
- Overall

Part C (MAD – HBeAg+):

- VIR-2218 50 mg
- VIR-2218 200 mg
- VIR-2218 Overall
- Placebo

- Overall

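### The dose-proportionality rule applies limits around a slope of 1 to dose-normalized PK parameters, for which proportionality means a slope of 0

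*SAP*

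**What the plan says.** SAP Section 9.6 applies to AUC0-inf, AUC0-t, AUC0-12, AUC0-24 and Cmax, separately for Part A and for the day-1 dose in Parts B and C.

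- **Response variable:** "To assess dose proportionality, the natural log transformed, dose normalized" values of those five parameters.
- **Model:** the "parameters will be evaluated using power model [2], with VIR-2218 dose level as the independent variable". The equation is log(y) = log(β0) + β1 log(Dose), "where y represents the PK parameter of interest".
- **Decision rule:** "Dose proportionality is concluded if 90% CI for the" slope β1 "falls within 0.7 to 1.43, which is less than 30% difference between doses for a given PK parameter".

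No other text resolves the point. SAP Section 15 records no changes to the planned analysis. Protocol Section 9.6 describes the PK analysis but contains no proportionality rule to fall back on.

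**The concern.** The response variable and the acceptance limits belong to two different forms of the power model. Limits around 1 fit the raw parameter, where exposure proportional to dose gives a slope of 1. For a parameter already divided by dose, proportionality gives a flat line, so the limits would have to surround 0.

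A programmer who follows the text literally would divide by dose, fit the model and compare the slope with 0.7 to 1.43. Proportional data would then be reported as not proportional, and strongly supra-proportional data could be reported as proportional. This affects all five parameters in both evaluations. SAP Section 16.1 also plans subject-level unblinding at the first interim analysis. If the mismatch is noticed only after that, choosing which half of the rule to change becomes a post hoc decision.

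**Working it through.** **Inputs**

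- Limits 0.7 and 1.43, 90% interval: SAP 9.6.
- Part A doses: 50, 100, 200 and 400 mg planned (SAP 2.5). SAP 3.6 adds 600 mg and "VIR-2218 900 mg".
- Part B doses: 20, 50, 100 and 200 mg (SAP 3.6).
- Active subjects per cohort: 6 in Part A (1 sentinel plus 5 of the remaining 6; Protocol 1.3) and 3 of 4 in Part B (SAP 2.1).
- Between-subject CV: not in the documents. Values of 20% to 70% are assumed.

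**1. Where the limits come from.** 1 - 0.30 = 0.70 and 1/0.70 = 1.4286, which rounds to 1.43. Their geometric centre is √(0.7 × 1.43) = 1.0005. The limits are therefore built around a slope of 1.

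**2. What normalization does to the slope.** Let exposure = c × Dose^k. Then:

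- raw parameter: ln(exposure) = ln(c) + k ln(Dose), so β1 = k;
- dose-normalized: ln(exposure/Dose) = ln(c) + (k - 1) ln(Dose), so β1 = k - 1.

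| True kinetics | k | β1, raw | β1, dose-normalized | Normalized β1 within 0.7 to 1.43? |
|---|---|---|---|---|
| Proportional | 1 | 1 | 0 | No |
| Dose squared | 2 | 2 | 1 | Yes |

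A noise-free least-squares fit over 50 to 900 mg returned the same four slopes.

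**3. What the rule accepts as written.** 0.7 ≤ k - 1 ≤ 1.43 gives 1.70 ≤ k ≤ 2.43. The range 50 to 900 mg is 18-fold. The accepted rise in exposure is 18^1.70 = 136-fold to 18^2.43 = 1,123-fold, against 18-fold under proportionality.

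**4. Behaviour in finite samples.** Log-normal error with SD √ln(1 + CV²), a 90% t-interval for the slope, and 20,000 simulated trials per scenario. The table shows the share of trials concluding proportionality.

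| Layout | CV | Proportional, as written | Dose squared, as written | Proportional, raw parameter | Dose squared, raw parameter |
|---|---|---|---|---|---|
| Part A, 4 planned doses × 6 | 20% | 0% | 100% | 100% | 0% |
| | 30% | 0% | 98.3% | 98.3% | 0% |
| | 50% | 0% | 70.8% | 71.2% | 0% |
| Part A, 6 doses × 6 | 20% | 0% | 100% | 100% | 0% |
| | 30% | 0% | 100% | 100% | 0% |
| | 50% | 0% | 98.3% | 98.2% | 0% |
| Part B, 4 doses × 3 | 20% | 0% | 99.5% | 99.4% | 0% |
| | 30% | 0% | 86.9% | 86.9% | 0% |
| | 50% | 0% | 36.0% | 36.6% | 0% |

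At an assumed CV of 70%, dose-squared kinetics passed the rule as written in 87% of trials (Part A, six doses), about 35% (Part A, four doses) and about 9% to 10% (Part B). Proportional kinetics still passed in 0%.

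**The case against.** The strongest reply is that Section 9.6 describes the response twice. The sentence giving the equation says only "where y represents the PK parameter of interest", and SAP Section 9 defines Cmax and the AUCs without dividing by dose. On that reading the equation, the definition of y and the limits agree, and only the two introductory words are out of place. That may well be what was meant. It does not remove the problem: the later phrase does not withdraw the explicit instruction, and under either reading one sentence has to change.

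Three further points narrow the claim.

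- **The conclusion does not always flip.** For true exponents below 0.70, between 1.43 and 1.70, or above 2.43, the true slope lies outside the limits under both versions. With small cohorts and high variability, wide intervals often fail both: in Part B at a CV of 50%, even the corrected rule passes proportional kinetics in only about 37% of trials.
- **Dose-squared kinetics are an illustration.** Nothing in the documents suggests that VIR-2218 behaves that way. The six-dose result for Part A also includes the two optional cohorts.
- **The consequence is limited.** Dose proportionality is not a listed endpoint, SAP 3.3 plans no formal hypothesis testing, PK parameters are summarized regardless, and dose escalation rests on committee review rather than on this rule. A pharmacokineticist would probably recognize a slope near 0.

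These points limit how often a wrong label would appear and how much would follow from it. They do not make the rule correct. It is still a pass/fail conclusion on data serving the secondary PK objective, and it cannot be met by truly proportional kinetics of any realistic precision.

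**Conclusion.** The concern holds. As written, the response variable and the acceptance limits in SAP 9.6 are incompatible, and the offset is exactly 1 on the slope scale. This is algebra and needs no assumption about variability.

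The rejection of proportional kinetics appeared in every simulated scenario (0% passing). False acceptance of dose-squared kinetics is exact for the true slope, but in a finite sample it depends on the dose range, cohort size and assumed CV. Across CVs of 20% to 50% it ran from 71% to 100% in Part A and from 36% to 99.5% in Part B, and it was lower at a CV of 70%. The error should be corrected before the rule is applied to any data.

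**What to change.** Preferred: delete the words *dose normalized* from SAP 9.6, so that ln(parameter) is regressed on ln(dose) and the slope is compared with limits around 1. Stating in the same sentence that y is the un-normalized parameter would remove any doubt.

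Alternative: keep the dose-normalized response and move both limits down by 1, from 0.7 and 1.43 to -0.30 and 0.43. The two versions are algebraically the same test.

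Either change is a small text edit to the SAP, with no new data and no change to study conduct.

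A separate matter to settle at the same time: even for raw parameters, a slope within 0.7 to 1.43 does not keep differences between doses below 30% over these ranges. The implied ratio of dose-normalized exposure, r^(β1 - 1), spans 0.54 to 2.45 over the 8-fold range 50 to 400 mg and 0.42 to 3.47 over 50 to 900 mg. Holding that ratio within 0.70 to 1.43 would need slope limits of 1 ± ln(1/0.7)/ln(r): about 0.83 to 1.17 for r = 8 and 0.88 to 1.12 for r = 18. That would be a change of criterion, with some loss of power, and the correction above does not depend on it.

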3.3 Hypothesis Testing and Inferential Analyses

Descriptive statistics will be used to summarize all data. No formal hypothesis testing is planned.

3.4 Multiple Comparisons and Multiplicity Adjustments.

Not applicable for this study.

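### SAP 9.6: slope limits of 0.7 to 1.43 do not mean less than a 30% difference between doses, and they do not fit a dose-normalized response

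*SAP*

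**What the plan says.** SAP 9.6 fits the log of a PK parameter (C_max and four AUCs) against log dose, with slope β1. It opens the method with "To assess dose proportionality, the natural log transformed, dose normalized" parameters, so the response is described as already divided by dose. The rule follows: "Dose proportionality is concluded if 90% CI for the" slope "falls within 0.7 to 1.43, which is less than 30% difference between doses for a given PK parameter". The limits are fixed and do not refer to the dose range.

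Two groups are analysed: "Dose proportionality will be evaluated separately for healthy subjects (part A) and day-1 dose of CHB subjects (part B and C"). SAP 2.5 gives the planned Part A doses: "Four dose-level cohorts are planned for Part A: 50 mg, 100 mg, 200 mg, and 400 mg". SAP 3.6 takes Part A up to "VIR-2218 900 mg". It lists Part B at 20, 50, 100 and 200 mg and Part C at 50 and 200 mg.

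SAP 3.3 describes the plan as non-inferential: "Descriptive statistics will be used to summarize all data. No formal hypothesis testing is planned".

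**The concern.** The limits 0.7 and 1.43 are reciprocals (1/0.7 = 1.4286). That is the usual form of limits for a ratio of exposures, not for a slope. It is an inference that they were carried over from a ratio criterion, and the arithmetic does not depend on it. A slope is an exponent: the same slope implies a small departure over a narrow dose range and a large one over a wide range. The stated 30% therefore cannot hold for every range to which the rule is applied.

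The response variable raises a second problem. If exposure is divided by dose before modelling, proportional kinetics give a slope of 0, and the rule would reject exactly the behaviour it is meant to detect.

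At stake is a statement in the study report that proportionality was shown to within 30% when the rule does not show it.

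**Working it through.** **Inputs.** Rule: 90% CI for β1 inside 0.7–1.43 (SAP 9.6). Dose ranges r = highest/lowest (SAP 2.5 and 3.6):
- Part A, all listed doses: 900/50 = 18
- Part A, planned doses: 400/50 = 8
- Part B, or B and C pooled: 200/20 = 10
- Part C alone: 200/50 = 4

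**Step 1: can the 30% be reproduced?** Take y as not dose normalized, the only reading under which limits around 1 make sense. Then y = β0·Dose^β1, and the ratio of dose-normalized exposures across a range r is r^(β1 − 1). At the limits this is r^(−0.30) and r^(0.43).

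| Range | r | At slope 0.7 | At slope 1.43 |
|---|---|---|---|
| Part A 50–900 mg | 18 | 0.420 | 3.466 |
| Part A 50–400 mg | 8 | 0.536 | 2.445 |
| Parts B/C 20–200 mg | 10 | 0.501 | 2.692 |
| Part C 50–200 mg | 4 | 0.660 | 1.815 |

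The stated figure is not reproduced for any range. The largest r for which the ratio stays within 0.70–1.43 is 0.7^(−1/0.30) = 3.28 at the lower limit and (1/0.7)^(1/0.43) = 2.29 at the upper.

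**Step 2: adjacent doses only.**
- 2-fold step: 0.812 to 1.347
- 1.5-fold step: 0.885 to 1.190
- 2.5-fold step (20 to 50 mg): 0.760 to 1.483
- 4-fold step (Part C alone): 0.660 to 1.815

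All Part A steps stay within 0.70–1.43. The 20 to 50 mg step does not, and neither does Part C taken alone. Against a literal +30%, the 2-fold step also exceeds it.

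**Step 3: dose-normalized response, as written.** The ratio becomes r^β1 and proportionality is β1 = 0. At r = 18, slopes of 0.7 and 1.43 mean that dose-normalized exposure rises 7.6-fold and 62-fold. Truly proportional kinetics pass 0% of the time in every design simulated below.

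**Step 4: how often do non-proportional slopes pass?** The documents give no PK variability, so between-subject CVs of 20%, 30% and 50% are assumed. Log exposure was simulated on log dose with log-normal error, SD = √ln(1 + CV²), and a 90% t-interval on n − 2 df that had to lie wholly inside the limits (40,000 regressions per scenario). Active subjects per dose follow the allocation: Part A 1 + 5 = 6, Parts B and C 3 each. Floaters are left out.

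| Design | Slope 0.8: change over range | Passes (CV 20/30/50%) | Slope 1.3: change over range | Passes (CV 20/30/50%) |
|---|---|---|---|---|
| Part A, 6 doses × 6 | 18^(−0.2) = 0.56 | 91 / 64 / 35% | 18^0.3 = 2.38 | 99 / 84 / 50% |
| Part A, 4 doses × 6 | 8^(−0.2) = 0.66 | 59 / 34 / 19% | 8^0.3 = 1.87 | 78 / 49 / 26% |
| Part B, 4 doses × 3 | 10^(−0.2) = 0.63 | 40 / 24 / 13% | 10^0.3 = 2.00 | 56 / 33 / 16% |
| B and C pooled (3/6/3/6) | 0.63 | 52 / 31 / 17% | 2.00 | 71 / 43 / 23% |

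A true slope exactly at a limit passes about 5% of the time, so the Step 1 ratios are boundary values, not typical passing results.

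**Step 5: slope limits that would match 0.70–1.43 on the ratio.** These are 1 ± ln(1/0.7)/ln(r):
- r = 18: 0.877–1.123
- r = 8: 0.828–1.172
- r = 10: 0.845–1.155

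**The case against.** The best defence is that the phrase about differences between doses is ambiguous. Read as adjacent doses, the statement works throughout Part A on the 0.70–1.43 scale. SAP 9.6 also appears to treat Parts B and C as one group, so the Part C step of 50 to 200 mg is not a separate analysis. That leaves one failing step, 20 to 50 mg, at 1.48 against 1.43. This narrows the fault but does not remove it: the pooled range is still 20–200 mg, and a slope rule concerns the whole fitted range.

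The reference to dose normalization may be only a drafting slip, since the equation's y is the PK parameter itself and the limits sit around 1. A 0% pass rate would probably be noticed at the first fit. That is fair, but the text still tells the programmer to do something that does not fit the rule.

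The pass rates depend on assumed CVs. They exceed one half mainly in six-dose Part A or at a CV of 20%, and none exceeds 50% at a CV of 50%. That stands, but the error in the stated meaning needs no CV.

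Finally, dose proportionality is not a listed objective or endpoint, and nothing in the documents makes escalation depend on it. That also stands and limits the severity.

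**Conclusion.** The concern holds. The stated equivalence between the slope limits and a difference below 30% is wrong for every full dose range in the SAP, whether or not Parts B and C are pooled. At the limits, dose-normalized exposure may fall by 58% or rise 3.5-fold over 50–900 mg, and fall by 46% or rise 2.4-fold over the planned Part A doses. Separately, a dose-normalized response cannot be paired with limits around 1.

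These two conclusions rest only on the power model and the listed doses. The size of the practical risk rests on the assumed CVs: in six-dose Part A, a 44% shortfall across the range would be called proportional in 35% to 91% of trials. The point should be fixed, but it affects the label on a secondary PK summary, not the trial's primary conclusions.

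**What to change.** In SAP 9.6:

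1. State that the power model is fitted to the natural log of the parameter without dose normalization, so that proportionality is a slope of 1.
2. Report the slope with its 90% CI, and r^(slope − 1) with its 90% CI, where r is the highest over the lowest dose actually given. Do this for Part A and for Day 1 of Parts B/C, and say outright whether B and C are pooled.
3. Delete the 0.7–1.43 yes/no rule and the 30% statement. This also fits the descriptive intent of SAP 3.3.

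If a yes/no rule is wanted, apply 0.70–1.43 to the 90% CI of r^(slope − 1), using the slope limits in Step 5, and describe a failure as inconclusive, not as non-proportional.

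The change is wording only and needs no new data. The descriptive version gives up a yes/no statement. The corrected rule would often be inconclusive even for truly proportional kinetics. Its pass rates at assumed CVs of 20/30/50% are:
- Part A, six doses: 96 / 60 / 3%
- Part A, four doses: 88 / 39 / 1%
- Part B: 40 / 6 / 0.2%
- B and C pooled: 67 / 15 / 0.2%

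That is why descriptive reporting is the better choice here.
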